
Primary Objectives:

1. To explore whether receipt of IIV during the second week of the menstrual cycle (i.e., the week prior to ovulation) is associated with changes in steroid hormone levels, particularly decreases in progesterone, following ovulation.
2. To assess the feasibility of conducting further research in this area.

Primary Endpoints:

1. Changes in levels of estradiol and progesterone one week after receipt of influenza vaccination.

Exploratory Objectives:

1. To explore whether inflammatory cytokine responses to IIV receipt are associated with changes in reproductive hormone levels.
2. Identify optimal biomarkers of the inflammatory response after vaccination.
3. To collect peripheral blood mononuclear cells (PBMC) for future studies of cellular immune response.

Exploratory Endpoints:

1. Assess the inflammatory cytokine responses (including C-reactive protein [CRP]) to IIV.
2. To record adverse events in the 7 days after vaccination, including fever, myalgia, malaise, and hypersensitivity reactions.

II. Background and Rationale: Explain why this study is being done. Summarize briefly what is already known about the issue and reference previously published research, if relevant.

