1. Women 18-39 years of age who are in good health.

2. Good general health as a result of review of medical history and/or clinical testing at the time of screening.
3. Available for the duration of the trial.
4. Willingness to participate in the study as evidenced by signing the informed consent document.
5. Willing to be abstinent or to use non-hormonal methods of contraception for the duration of the study.
6. History of normal menstrual cycles (26 to <35 days in length) for ≥3 months prior to enrollment.
7. Willingness to refrain from routine vaccination (except as administered during study) for the duration of the study.

B. Exclusion Criteria:

1. Use of contraceptive pills, patch, injection or other hormonal therapies in the preceding 3 months. Or 6 months for Depo-Provera.
 2. A history of hypersensitivity, including anaphylaxis to any of the components of IIV or to eggs.
 3. Previous receipt of the same-season influenza vaccine.
 4. Pregnancy as determined by a positive urine or serum human chorionic gonadotropin (β-hCG) test at any point during the study or in the preceding 3 months.
 5. Currently is lactating or breast-feeding.
 6. Fewer than 3 normal menstrual cycles since conclusion of last pregnancy or last use of hormonal birth control.
 7. A history of autoimmune disease, or any other chronic medical condition considered clinically significant by the investigator.
 8. History of HIV, Hepatitis C or active Hepatitis B.
 9. Known immunodeficiency syndrome.
 10. History of Guillain-Barré syndrome.
 11. Use of chronic oral or intravenous administration (≥14 days) of immunosuppressive doses of steroids, i.e., prednisone >10 mg per day, immunosuppressants or other immune-modifying drugs within 30 days of starting this study. (Use of topical, nasal or inhaled steroids is permitted)
 12. Receipt of a live vaccine within 4 weeks or a killed vaccine within 2 weeks prior to study start or during study.
 13. Receipt of blood or blood-derived products (including immunoglobulin) within 6 months prior to study vaccination.
 14. Receipt of another investigational vaccine or drug within 30 days prior to study start, or during study.
 15. Ongoing, daily use of analgesics or anti-inflammatory medications, including nonsteroidal anti-inflammatories. Occasional use, and use associated with menstrual periods is acceptable.

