1. Obtain blood for measurement of cytokines.

Day 17 +/-2 days (after ovulation), Day 21 +/- 2 days

Day 28 +/- 5 days (1st day of menstrual cycle)

1. Collect brief history of any new illnesses or problems since last visit
2. Review pregnancy prevention counseling.
3. Obtain blood for measurement of progesterone, and estradiol.

Day 21 +/- 2 days:

1. Collect approximately 30 cc of blood for PBMC processing.

Day 38-45

1. Participant to utilize LH strip at home, and call study staff when positive.
2. Participant to record on memory card results of LH strip.

Day 39 +/- 3 days (~ 11 days after menstruation; prior to ovulation)

1. Collect brief history of any new illnesses or problems since last visit
2. Review pregnancy prevention counseling.
3. Obtain blood for measurement of progesterone, estradiol, baseline cytokines and Hemagglutination Inhibition Assay (HAI).
4. Obtain approximately 30 cc of blood for PBMC processing.
5. Check urine pregnancy test.
6. Vaccinate subject with IIV.

Day 40 +/-1 day (1 day after vaccination), Day 41 +/-1 day (2 days after vaccination)

1. Collect brief history of any new illnesses or problems since last visit, ask about adverse events after vaccination.
2. Review pregnancy prevention counseling.
3. Obtain blood for measurement of cytokines.
Days 41-43 (2-4 days after vaccination).

Subject to answer questions reactivity in the REDCap database or on the memory card.

Day 45 +/-1 day (6-8 days after vaccination), Day 49 +/- 1 day (10-12 days after vaccination)

1. Collect brief history of any new illnesses or problems since last visit; ask about adverse events after vaccination.
2. Review pregnancy prevention counseling.
3. Obtain blood for measurement of progesterone, and estradiol.

Day 49 +/- 1 day (10-12 days after vaccination)

1. Obtain approximately 30 cc for PBMC processing.

Day 56 +/-4 days (1st day of menstruation)

1. Get brief history of any new illnesses or problems since last visit.
 2. Check urine pregnancy test.
 3. Obtain blood for measurement of progesterone, estradiol and for HAI.
3. Describe the expected duration of the study from the perspective of the individual participant and duration overall.

Each participant will spend about 3-4 months in the study, from screening to completion.
Each subject will be expected to come to approximately 14 visits

4. Provide a brief data analysis plan and a description of variables to be derived.

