The data will be analyzed using the computer software STATA (version 13, Stata Corp, College Station, TX). Each participant will serve as her own control. Summary data of the baseline characteristics of participants will be described using mean (SD) and median for continuous variables or frequencies and proportions for categorical data, as appropriate. Vaccine HAI titers will be measured prior to vaccination (day 39) and at 17 days following vaccination (day 56)

PA1: To determine if vaccination with IIV prior to ovulation (day 11 of menstruation) is associated with changes in post-ovulation serum reproductive (progesterone and estradiol) hormone concentrations.

-H 1: Post-vaccination serum reproductive hormone concentrations will be lower in the post-vaccination cycle than measured prior to vaccination.

The skewness of the hormone concentration distributions will be checked using Kolmogorov-Smirnov test or Shapiro-Wilks test. Transformation of the non-normal data to achieve normality will be attempted using natural logarithms or other mathematical functions. In the event that power transformations fail to normalize the data then non-parametric tests will be used. The mean difference (SD) between pre-vaccination serum hormone (progesterone and estradiol) concentrations and post-vaccination serum hormone concentrations measured during the luteal phase (days 17, 21, 28) of menstruation for each participant will be estimated using paired t-test for parametric data or by the Wilcoxon matched-pairs signed rank sum test for non-parametric data. A p-value < 0.05 will be considered statistically significant in all analyses. Stratified analyses will be conducted to determine if host characteristics modify the effects of vaccination on hormonal responses.

EA1: To determine if serum inflammatory biomarker (cytokines, chemokines, and C-reactive protein) concentrations differ following vaccination with IIV.

-H2: Serum pro-inflammatory biomarker concentrations at 24- and 48-hours post vaccination will be increased relative to baseline concentrations.

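### The primary endpoint is set at one week after vaccination, but PA1 adds two later days for both hormones, gives no rule for one pair per woman, and does not say which test is primary

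*Protocol*

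**What the plan says.** - **Endpoint.** Protocol, Primary Endpoints, has one entry: "Changes in levels of estradiol and progesterone one week after receipt of influenza vaccination".
- **Visit that fits it.** The visit list (Section V, Study Implementation) has "Day 45 +/-1 day (6-8 days after vaccination"). The next hormone visit, Day 49, is labelled 10-12 days after vaccination, and the data analysis plan puts Day 56 at 17 days after.
- **Analysis.** PA1 in the data analysis plan (Study Implementation, item 4) takes the mean pre/post difference in progesterone and estradiol "measured during the luteal phase (days 17, 21, 28) of menstruation for each participant will be estimated using paired t-test for parametric data", or the Wilcoxon signed-rank test otherwise. The threshold is "A p-value < 0.05 will be considered statistically significant in all analyses".
- **Hypothesis.** H1 under PA1 reads "Post-vaccination serum reproductive hormone concentrations will be lower in the post-vaccination cycle than measured prior to vaccination". H1 in the Protocol's sample size section (III.B) and in the SAP names progesterone only.
- **Day 28.** PA1 counts it as luteal. The visit list has "Day 28 +/- 5 days (1st day of menstrual cycle") and, for its counterpart in the vaccinated cycle, "Day 56 +/-4 days (1st day of menstruation").
- **Power.** Section III.B and the SAP give the same table for 90 women. Its inputs are described only as luteal-phase progesterone, with no day or summary. The SAP contains nothing beyond this calculation.

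**The concern.** A paired t-test or signed-rank test takes one difference per woman. PA1 supplies three days for each of two hormones and does not say whether the days are averaged, summarised in some other way, or tested one by one. It does not say which hormone carries H1 or what happens if the results disagree. The endpoint points to one day, PA1 to three, and the power calculation to an unnamed luteal value.

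Which day, summary or hormone counts as the primary result could therefore be settled after the data are seen. If more than one comparison is made at 0.05, the chance of at least one false claim rises above the nominal level. The stated power belongs to a single test that the plan does not identify. Any merged luteal value would also include samples that the schedule places at the start of the next cycle.

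**Working it through.** **1. Match the endpoint to the schedule.** On a 28-day count, the vaccinated-cycle visits correspond to 45-28=17, 49-28=21 and 56-28=28. Only Day 45, with counterpart Day 17, is about one week after vaccination. PA1 therefore contains the endpoint visit and adds two later ones.

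**2. Reproduce the power table.** Inputs from Section III.B and the SAP: log10 SDs 0.51 and 0.54, correlation 0.60, n=90, type-1 error 0.05 (sidedness not stated).

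SD of the paired difference = sqrt(0.51² + 0.54² - 2×0.60×0.51×0.54) = sqrt(0.2212) = 0.470.

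Noncentrality = |log10(ratio)| × sqrt(90) / 0.470, with 89 degrees of freedom, two-sided 0.05:

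| Median ratio | Noncentrality | Recomputed power | Stated power |
|---|---|---|---|
| 0.75 | 2.52 | 0.703 | 0.69 |
| 0.70 | 3.12 | 0.871 | 0.86 |
| 0.65 | 3.77 | 0.962 | 0.95 |

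A one-sided test would give 0.804 at ratio 0.75, so the table describes one two-sided paired test. Over all nine cells, eight agree within 2 points. The exception is 0.652 against 0.63 (ratio 0.75, correlation 0.55). With SD 0.54 in both cycles, all nine agree.

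**3. Which day gave the inputs?** The introduction ties a 20% fall in progesterone to day 17. The sample size section plans from a 26% fall (10^-0.13 = 0.74) in the luteal phase. These may differ by day or by statistic; the documents do not say.

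**4. Chance of at least one false claim.** With k independent tests at 0.05 it is 1-0.95^k. Counting only false decreases, the direction of H1, it is 1-0.975^k. For correlated tests I used normal test statistics with a common correlation. The documents give no correlation between days or hormones, so 0, 0.5 and 0.9 are assumptions.

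| Reading of PA1 | Tests | Any false claim (0 / 0.5 / 0.9) | False decrease only (0 / 0.5 / 0.9) |
|---|---|---|---|
| One test | 1 | 5% | 2.5% |
| Days merged, two hormones | 2 | 9.8% / 9.1% / 7.0% | 4.9% / 4.5% / 3.5% |
| Progesterone, three days | 3 | 14% / 13% / 8% | 7% / 6% / 4% |
| Two hormones, three days | 6 | 26% / 21% / 11% | 14% / 10% / 5% |

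**5. Cost of splitting alpha equally instead of ordering the tests.** At ratio 0.75 and correlation 0.60, power falls from 0.70 to 0.53 at 0.05/3 and to 0.43 at 0.05/6, if the planning SDs apply to the day tested.

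**6. Day 28.** The inclusion criterion is "History of normal menstrual cycles (26 to <35 days in length"), and the windows are ±5 days at Day 28 and ±4 days at Day 56. Some of these samples may still precede menses, so the conflict lies in the labels and need not affect every sample.

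**The case against.** The strongest reply is that this is an exploratory study with an evident lead outcome. The primary objective is worded as exploration, sits beside a feasibility aim, and singles out decreases in progesterone; the sample size rests on progesterone alone. One luteal value per woman is as natural a reading of PA1 as three separate days.

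Much of this stands. It limits the severity and makes six separate tests the most adverse reading. It does not remove the gap: PA1 states a directional hypothesis with a significance threshold, the sample size is justified by power for that aim, and the endpoint and PA1 both name two hormones. If one luteal value is meant, its formula is missing.

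A reader might also infer more than the documents support:

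- That PA1 abandons the stated endpoint. It does not; Day 17 is in its list.
- That any single significant result would confirm H1. No sentence says so. The plan leaves the rule unstated.
- That Day 28 samples are all taken in menses. The windows and eligible cycle lengths contradict this.

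A practical objection concerns matching on exact cycle day. After a 28-day first cycle, vaccination at Day 39 ±3 falls on cycle day 8-14, so a draw 6-8 days later falls on cycle day 14-22, while the Day 17 ±2 control draw covers 15-19. Exact pairs will not exist for every woman, so matching must be by visit. The printed interval also needs reconciling with the day numbers (45-39=6, so ±1 day gives 5-7), but either interval includes one week.

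**Conclusion.** The point holds and should be fixed. Endpoint, analysis, hypothesis and power calculation do not identify the same primary test, and the Day 28 labels conflict.

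The size depends on how PA1 is read. The chance of at least one false claim is up to 9.8% with merged days and two hormones, 8-14% with three progesterone days, and 11-26% with all six. Counting only false decreases, these become up to 4.9%, 4-7% and 5-14%, against 2.5% for one two-sided test. The ranges rest on assumed correlations from 0.9 to 0.

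The 26% should not be quoted as the plan's error rate. It needs six separate tests and independence, which is implausible for serial samples from the same women. Nor is the power table wrong: it is sound for one paired progesterone value that remains to be named.

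**What to change.** In PA1 and the SAP:

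1. Name one primary paired comparison of log progesterone: the one-week post-vaccination visit (Day 45) against its scheduled counterpart (Day 17) in the unvaccinated cycle, matched by visit, whichever cycle comes first. If the sponsor prefers a prespecified mean of Days 17 and 21 (45 and 49), change the primary endpoint to match.
2. Test estradiol second, at 0.05, only if progesterone is significant. Make other days secondary. Keep Days 28/56 out of the primary luteal comparison and report them descriptively.
3. State H1 identically in the sample size section, PA1 and the SAP.
4. State which day or summary gave the pilot SDs and correlation, and recompute the power table if it differs from the primary test.
5. Disclose that the pilot Day 17 result is already known for 30 of the 90 women, and add a sensitivity analysis in the women enrolled after the pilot.

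The cost is wording, a check of the pilot data and one extra analysis, with no new samples. Progesterone keeps the full 0.05. On the downside, an effect seen only on a later day or only in estradiol could not be claimed as primary. Some Day 17/45 samples may precede ovulation, since home LH testing runs through those days. A mean of two days could have more power if the effect is equal on both.

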The power calculations are based on specific aim 1, with regards to changes in progesterone.

SA1: To determine if vaccination with IIV prior to ovulation (day 11 of menstruation) is associated with changes in post-ovulation serum reproductive (progesterone and estradiol) hormone concentrations.

-H 1: Post-vaccination serum progesterone concentrations will be lower in the month after vaccination than measured prior to vaccination.

We are planning to study 30 adult non-pregnant women each year. Based on the results from the first 30 student enrollees, we estimate the log (base 10) mean (SD) serum concentration of progesterone during the luteal phase of menstruation prior to vaccination is 0.71 (□ 0.51), and 0.58 (□ 0.54) post vaccination. This difference of -0.13 on the log (base 10) scale corresponds to a median ratio of 0.74 in other words, a 26% decrease in median progesterone levels after vaccination. The observed correlation in these log concentration values was 0.60. For a total sample size of 90 women (base task order and 2 option years), assuming similar standard deviation in log (base 10) pre- and post- vaccination values as observed in the initial sample of 30, the following table shows to the power to detect a given median post-vaccination to pre-vaccination concentration ratio for several pre- and post- concentration correlation values. These results are based on a type-1 error level of .05.

Median Ratio	Correlation		
	0.55	0.60	0.65
0.75	0.63*	0.69	0.74
0.70	0.82	0.86	0.90
0.65	0.93	0.95	0.97

* values in italics give estimated power to detect the specified median ratio for a specified correlation between the pre- and post-vaccination progesterone values

IV. Participants:

Describe the study participants and the population from which they will be drawn. Specify the inclusion and exclusion criteria. If you plan to include children, note their ages and whether you will include children in foster care. Note if the participants are particularly vulnerable in terms of cognitive limitations, education, legal migration status, incarceration, poverty, or some combination of factors.

Women aged 18-39 years will be recruited from Johns Hopkins University Campuses as well as from the surrounding community in East Baltimore. We will aim to include approximately equal numbers of women who have and have not previously received an H1N1-containing influenza vaccine.

A. Inclusion Criteria:

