The skewness of the cytokine concentration distributions will be checked using Kolmogorov-Smirnov test of normality. Transformation of the non-normal data to achieve normality will be attempted using natural logarithms. In the event that natural logarithm transformation fails to normalize the data then non-parametric tests will be used. Relationships between the different inflammatory biomarkers interest will be analyzed using Pearson's correlation or with Spearman's rank test, as needed. The mean difference (SD) in cytokine concentrations between baseline and at 24 hours post-vaccination, and between baseline and 48 hours post-vaccination within individuals will be evaluated by paired t-test for parametric data or by the Wilcoxon matched-pairs signed rank sum test for non-parametric data. Stratified analyses will be used to determine if host characteristics

modify the effects of vaccination on hormonal responses. Our study design will also allow us to look at differences in cytokines at various points in the nonvaccination menstrual cycle.

EA2: To determine if post-vaccination inflammatory biomarker responses to IIV receipt (days 40 and 41) are associated with changes in reproductive hormone levels during the second menstrual cycle.

-H3: Changes in serum pro-inflammatory responses between baseline and 24(and/or 48)-hours post-vaccination, will be inversely correlated with serum reproductive hormone concentrations during the second menstrual cycle.

Correlations between changes in post-vaccination serum pro-inflammatory biomarkers (days 39 to 40, 39 to 41) and changes in serum hormone responses during the second menstrual cycle (days 45 to 49, 45 to 56), will be calculated using Pearson's correlation coefficient and evaluated using the paired t-test for parametric data or Spearman's rank correlation test and the Wilcoxon matched-pairs signed rank sum test for non-parametric data. In addition, we will correlate changes in the hormone levels observed in the second cycle to the first cycle (days 17 to 21, 17 to 28) using the same analytical techniques.

EA4: To describe the frequency of adverse events in the 7 days after vaccination, including fever, myalgia, malaise, and hypersensitivity reactions, and to determine if these adverse events are associated with cytokines responses.

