-H4: Adverse events, specifically fever, myalgia and malaise after vaccination, are associated with a greater inflammatory cytokine response than seen in people who do not experience these events.

The frequency and proportion of participants who experience vaccine-associated adverse symptoms will be reported. In addition, differences in mean (SD) serum inflammatory biomarker concentrations at 24 and 48 post-vaccination and mean (SD) changes in serum concentrations following vaccination by adverse symptom status will be explored using t-tests.

5. **Answer the following if they are relevant to your study design:**

A. If the study has different arms, explain the process for assigning participants (intervention/control, case/control), including the sequence and timing of the assignment.

Subjects will be screened for eligibility based on their age, medical, vaccination and menstrual history, and birth control methods used. All participants will receive the same influenza vaccine. We will aim to enroll equal numbers of women who have received an H1N1 containing vaccine with influenza vaccine naïve women. This will allow us to compare responses of women with previous vaccination with those without prior history of vaccine.

B. If human biospecimens (blood, urine, saliva, etc.) will be collected, provide details about who will collect the specimen, the volume (ml) and frequency of collection, how the specimen will be used, stored, identified, and disposed of when the study is over. If specimens will be collected for use in future research (beyond this study), complete the "Biospecimen Repository" section below.

Specimens will be collected by the PI, nurses and staff trained in the proper collection of samples and blood draws. Serum specimens will be collected during this study. Any remaining specimens at the conclusion of the study will be retained under the CIR biorepository protocol (CIR 213 IRB Number R.22.05.04.29.A2.)

- C. If genetic/genomic analyses are planned, address whether the data will be contributed to a GWAS or other large dataset. Address returning unanticipated incidental genetic findings to study participants.

N/A

- D. If clinical or laboratory work will be performed at JHU/JHH, provide the JH Biosafety Registration Number.

N/A

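### Stratified analyses are meant to decide whether host characteristics modify the vaccine effect on hormones, but no between-stratum test is stated; one should be written in.

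*Protocol*

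**What the plan says.** Protocol section V, Study Implementation, item 4 (data analysis plan), states under PA1: "Stratified analyses will be conducted to determine if host characteristics modify the effects of vaccination on hormonal responses". EA1 repeats the intention, again for hormonal responses: "Stratified analyses will be used to determine if host characteristics". Neither place lists the characteristics, the cut-points, the test within strata or the rule for comparing strata.

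For the hormone effect itself, PA1 says that the difference between the unvaccinated and vaccinated cycles "will be estimated using paired t-test for parametric data or by the Wilcoxon matched-pairs signed rank sum test for non-parametric data", and adds: "A p-value < 0.05 will be considered statistically significant in all analyses".

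One host characteristic has a planned split. Section IV (Participants) aims for "approximately equal numbers of women who have and have not previously received an H1N1-containing influenza vaccine". Item 5.A, after the analysis plan, gives the purpose: "This will allow us to compare responses of women with previous vaccination with those without prior history of vaccine". It names no test and does not say which responses are meant.

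The SAP contains only the power section and does not address effect modification.

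**The concern.** Effect modification is a difference between strata. A paired test inside one stratum asks only whether that stratum's effect differs from zero. A significant result in one stratum and a non-significant result in the other is therefore not evidence that the effects differ. Each stratum has about half the women, so its power is moderate, and that is where two strata with the same true effect most often fall on opposite sides of 0.05.

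At stake is a claim that progesterone falls after vaccination only in women with, or only in women without, some characteristic such as prior vaccination. The study's stated motive is vaccination around conception, so a spurious claim of this kind could mislead.

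**Working it through.** **Inputs** (Protocol III.B, repeated in the SAP): log10 progesterone SD 0.51 before and 0.54 after vaccination; correlation r = 0.60; 90 women; type-1 error 0.05, taken as two-sided because a one-sided test gives 0.80 where the plan's table has 0.69. Strata of 45 and 45 follow from the equal-numbers aim, which is stated for prior vaccination only.

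**Step 1: SD of the within-woman difference.**
sqrt(0.51² + 0.54² − 2 × 0.60 × 0.51 × 0.54) = sqrt(0.2212) = 0.470.

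**Step 2: reproduce the plan's figure.** Paired t-test, noncentral t, n = 90, ratio 0.75 (log10 = −0.125), r = 0.60: power 0.703, against 0.69 in the table. Across the nine cells, eight agree within 2 points. The ninth (ratio 0.75, r = 0.55) gives 0.652 against 0.63. With SD 0.54 at both times all nine agree within 1 point. The inputs are sound for what follows.

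**Step 3: separate paired tests, same true effect in both strata.** With power p in each stratum of 45, the chance that exactly one is significant is 2p(1 − p).

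| True ratio in both strata | Power per stratum (n = 45) | Exactly one significant |
|---|---|---|
| 0.65 | 0.742 | 38% |
| 0.70 | 0.580 | 49% |
| 0.74 (pilot) | 0.442 | 49% |
| 0.75 | 0.414 | 49% |
| 0.80 | 0.272 | 40% |
| 0.85 | 0.166 | 28% |
| 0.90 | 0.098 | 18% |
| 1.00 (no effect) | 0.050 | 9.5% |

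Example at 0.75: 2 × 0.414 × 0.586 = 0.485. With strata of 30 (60 women) at 0.75, p = 0.290 and the chance is 2 × 0.290 × 0.710 = 41%. For unequal strata at 0.74 it is p1(1 − p2) + p2(1 − p1): 52% for 60/30 and 57% for 70/20.

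**Step 4: between-stratum test.** Compare the within-woman log10 difference between strata with a two-sample t-test. In 200,000 simulated trials with a common effect of −0.13 it was significant in 4.98%, while exactly one separate paired test was significant in 49.4%. With no vaccine effect the figures were 5.0% and 9.5%.

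The 5% is per test. Five independent tests would give 1 − 0.95⁵ = 23% chance of at least one false interaction.

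**Step 5: what that test can detect.** SE = 0.470 × sqrt(2/45) = 0.099. For ratio 0.75 against 1.00 the expected difference is 0.125, or 1.26 SE, and power is 0.24. Power of 80% needs a ratio of ratios of about 0.53. For a difference of 0.13 it needs about 206 women per stratum.

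**The case against.** A reader might infer that the plan's stated method is to set a significant stratum beside a non-significant one. The documents do not say this. The paired-test sentence in PA1 describes the overall contrast between cycles, and a stratified analysis could also mean comparing estimates and intervals or testing heterogeneity. Under EA4 the plan does compare mean changes between groups with t-tests, by adverse symptom status. That covers inflammatory biomarkers and not hormones, so it leaves the gap open, but it makes it less safe to assume that the analysts would compare p-values.

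A reader might also infer that enrolment is balanced on prior vaccination in order to study hormone modification. Item 5.A speaks only of responses, and HAI and cytokines are measured too. The 45/45 split is an assumption for any other characteristic.

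The 40–49% range needs a sizeable common effect. The pilot decrease was not significant, and smaller effects give lower figures, as the table shows.

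Finally, the objectives are exploratory, effect modification is not a listed objective, endpoint or numbered hypothesis, and the protocol form asks only for a brief plan. This limits the consequence. It does not remove the gap, because the text gives these analyses the task of deciding on modification and provides no test that can do so.

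**Conclusion.** The point holds as a gap in specification with a known better method. The plan assigns a decision about effect modification to stratified analyses, and the only hormone-effect tests it names cannot make that decision.

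If strata were read by separate paired tests, an identical effect would give one significant and one non-significant stratum in 38–49% of trials at ratios from 0.65 to 0.80, in 18–28% at 0.90 to 0.85, and in 9.5% with no effect. This rests on three assumptions: the inferred reading rule, strata of 45 each, and the planning SDs and correlation holding within each stratum. The main paired comparison and the sample size are unaffected. The change should be made, but as a correction to a secondary, exploratory analysis.

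**What to change.** In PA1, and in the matching EA1 sentence, state that modification will be judged by regressing the within-woman log difference (vaccinated minus unvaccinated cycle, on the same luteal measure as the main test) on the host characteristic. Where the non-parametric fallback applies, use a rank-sum test of the within-woman differences between strata. Report the ratio of ratios with its 95% CI and p-value, labelled exploratory. Keep stratum estimates as description only.

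Name prior vaccination as the lead modifier, list any others with cut-points, and say that 5% applies per test and not across modifiers and two hormones. Reconcile the definition of prior vaccination: section IV sets recipients of an H1N1-containing vaccine against non-recipients, while item 5.A sets them against women naïve to influenza vaccine. A woman who has had only a vaccine without H1N1 is in the comparison group under the first and in neither group under the second.

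The cost is a few sentences and one regression, with no new data or visits. The downside is low power, about 0.24 for a ratio of 0.75 against 1.00, so few modifiers will be claimed. The text should say that a null interaction does not show equal effects.
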